### 7.2.5. Repeat Visit A

Repeat Visit A occurs 12 weeks following the Week 96 visit for active participants or 12 weeks following the Re-entry Day 1 visit for re-entry participants, and then reoccurs every 24 weeks thereafter.

Subjects will return to clinic and the following assessments will be conducted:

- Height
- Weight
- Brief physical exam
- Measure vital signs (blood pressure, temperature, pulse, and respiratory rate)
- Adverse event monitoring
- Use of concomitant medications

- C-SSRS Since Last Visit version. If the C-SSRS indicates imminent risk for suicidality, defined as the subject positively endorsing questions 4 or 5 of the suicidal ideation section or any suicidal behavior questions, discontinue study drug and refer for appropriate care.
- Receive and count remaining tablets in each returned bottle of investigational product to assess adherence to BID dosing.

All repeat visits can be  $\pm 10$  (ten) days for flexibility.

### 7.2.6. Repeat Visit B

Repeat Visit B occurs 12 weeks following the first Repeat Visit A, and then reoccurs every 24 weeks thereafter.

Subjects will return to clinic and the following assessments will be conducted:

- Vital signs (blood pressure, temperature, pulse, and respiratory rate)
- Height
- Weight
- Full physical exam
- Adverse event monitoring
- Use of concomitant medications
- Clinical laboratory tests (blood and urine)
- ECG
- C-SSRS Since Last Visit version. If the C-SSRS indicates imminent risk for suicidality, defined as the subject positively endorsing questions 4 or 5 of the suicidal ideation section or any suicidal behavior questions, discontinue study drug and refer for appropriate care.
- Receive and count remaining tablets in each returned bottle of investigational product to assess adherence to BID dosing.

All repeat visits can be  $\pm 10$  (ten) days for flexibility.

### 7.2.7. End of Study / Early Termination (ET) Visit

Subjects will return to clinic and the following assessments will be conducted:

- Vital signs (blood pressure, temperature, pulse, and respiratory rate)
- Height
- Weight

- Full physical exam
- Adverse event monitoring
- Use of concomitant medications
- Clinical laboratory tests (blood and urine)
- ECG
- C-SSRS Since Last Visit version. If the C-SSRS indicates imminent risk for suicidality, defined as the subject positively endorsing questions 4 or 5 of the suicidal ideation section or any suicidal behavior questions, refer for appropriate care.
- Receive and count remaining tablets in each returned bottle of investigational product to assess adherence to BID dosing.

### 7.2.8. Re-entry Day 1(Re-entry for Subjects Who Previously Completed)

Subjects who completed the final visit on the PTI-125-09 study on Amendment 1 or Amendment 2 will be eligible to re-enter this open-label extension study if the subject does not meet exclusion criterion.

Subjects will come to the clinic for a Re-entry Day 1 visit and the following will be conducted:

- Informed Consent
- Medical History- focused on any new conditions that occurred during the gap period between study completion and study re-entry
- Vital signs (blood pressure, temperature, pulse, and respiratory rate)
- Height
- Weight
- Full physical exam
- Adverse event monitoring
- Use of concomitant medications
- Clinical laboratory tests (blood and urine)
- ECG
- C-SSRS Since Last Visit version. If the C-SSRS indicates imminent risk for suicidality, defined as the subject positively endorsing questions 4 or 5 of the suicidal ideation section or any suicidal behavior questions, discontinue study drug and refer for appropriate care.
- Review of Inclusion and Exclusion criteria following all Re-entry Day 1

assessments and prior to dosing.

Subjects will be administered one (1) tablet of study drug at the clinic. Subjects will be discharged with their supply of study drug until the next visit. They will be instructed to take study drug twice daily, with or without food. A dose can be up to 4 hours late, but if a dose is missed, the next dose should NOT be doubled.

Follow-up visits will continue as indicated in Appendix C- Schedule of Events for Reentry Participants. For all follow-up visits, subjects will be instructed to bring their study drug bottle to the clinic and a new bottle of study drug will be dispensed (except at the Re-entry Week 4 visit if required).

# 7.2.9. Re-entry Week 4 (Only for Re-entry Day 1 Subjects Who Complete Re-entry Day 1 Visit >60 Days After Completing PTI-125-09)

Subjects who completed Re-entry Day 1 Visit >60 days after completing their original study participation of PTI-125-09 will have a visit performed 4 weeks after Re-entry Day 1.

Subjects will come to the clinic for a Re-entry Week 4 visit and the following will be conducted:

- Vital signs (blood pressure, temperature, pulse, and respiratory rate)
- Height
- Weight
- Brief physical exam
- Adverse event monitoring
- Use of concomitant medications
- Clinical laboratory tests (blood and urine)
- ECG
- C-SSRS Since Last Visit version. If the C-SSRS indicates imminent risk for suicidality, defined as the subject positively endorsing questions 4 or 5 of the suicidal ideation section or any suicidal behavior questions, discontinue study drug and refer for appropriate care.

For Re-entry Week 4, the bottle that was previously dispensed at Re-entry Day 1, will be returned to the subject following study drug accountability.

Follow-up visits will continue as indicated in Appendix C – Schedule of Events for Re-entry Participants, starting with Week 12. For all follow-up visits, subjects will be

instructed to bring their study drug bottle to the clinic and a new bottle of study drug will be dispensed.

Re-entry Week 4 visit can be  $\pm 10$  (ten) days for flexibility.

### 7.3. LABORATORY ASSESSMENTS

### 7.3.1. Clinical Laboratory Tests

The following clinical laboratory tests will be performed at Study Day 1, Weeks 24, 48, and 96, Re-entry Day 1 (if applicable), Re-entry Week 4 (if applicable), and Repeat Visit B until study end:

- Hematology: white blood cell (WBC) count with differential, red blood cell (RBC) count, hemoglobin, hematocrit, platelet count.
- Serum Chemistry: glucose, sodium, potassium, chloride, bicarbonate, calcium, phosphate, blood urea nitrogen (BUN), total bilirubin, creatinine, cholesterol, triglycerides, albumin, globulin, total protein, uric acid, alkaline phosphatase, alanine transaminase (ALT), aspartate transaminase (AST), gamma glutamyl transpeptidase (GGT), lactose dehydrogenase (LDH).
- Urinalysis: color, specific gravity, pH, protein, sugar, ketones, occult blood, creatinine clearance calculation by Cockcroft-Gault equation (without requiring a 24-h urine collection).

### 8. EARLY DISCONTINUATION

Subjects, Investigators, and the Sponsor may choose to have a subject discontinue study drug or study participation at any time, for any reason, and without prejudice.

The following must be completed and documented in the source documents and the electronic case report forms (eCRFs) for all subjects who discontinue the study early:

- The reason for early study discontinuation.
- Vital signs (blood pressure, temperature, pulse, and respiratory rate), height, weight, full physical exam, clinical laboratory tests, ECG, use of concomitant medications, and adverse events should be obtained at discharge prior to release.
- Administer the C-SSRS Since Last Visit version. If the C-SSRS indicates imminent
  risk for suicidality, defined as the subject positively endorsing questions 4 or 5 of the
  suicidal ideation section or any suicidal behavior questions, immediately contact the
  sponsor.

### 9. ADVERSE EVENTS/SERIOUS ADVERSE EVENTS

### 9.1. ADVERSE EVENTS - DEFINITION

An adverse event (AE) is any undesirable event that occurs to a subject during a study, whether or not that event is considered study drug-related. Monitoring for AEs will start at dosing. Examples include:

- Any treatment-emergent signs and symptoms (events that are marked by a change from the subject's baseline/entry status [e.g., an increase in severity or frequency of pre-existing abnormality or disorder])
- All reactions from study drug, an overdose, abuse of drug, withdrawal phenomena, sensitivity, or toxicity to study drug
- Apparently unrelated illnesses
- Injury or accidents (Note: if a medical condition is known to have caused the injury or accident, the medical condition and the accident should be reported as two separate medical events [e.g., for a fall secondary to dizziness, both "dizziness" and "fall" should be recorded separately])
- Extensions or exacerbations of symptoms, subjective subject-reported events, new clinically significant abnormalities in clinical laboratory, physiological testing, or physical examination

All AEs, whether or not related to the study drug, must be fully and completely documented on the AE page of the eCRF and in the subject's clinical chart.

In the event that a subject is withdrawn from the study because of an AE, it must be recorded on the eCRF as such. The subject should be followed and treated by the Investigator until the abnormal parameter or symptom has resolved or stabilized.

The Investigator must report all directly observed AEs and all spontaneously reported AEs. The Investigator will ask the subject a non-specific question (e.g., "Have you noticed anything different since your dose of the study medication?") to assess whether any AEs have been experienced since the last assessment. AEs will be identified and documented on the eCRF in appropriate medical terminology. The severity and the relationship to the study drug will be determined and reported on the eCRF (see below).

### 9.2. ADVERSE EVENTS - SEVERITY RATING

The severity of each AE should be characterized and then classified into one of three clearly defined categories as follows:

• Mild – the AE does not interfere in a significant manner with the subject's normal functioning level. It may be an annoyance.

- Moderate the AE produces some impairment of functioning but is not hazardous to health. It is uncomfortable or an embarrassment.
- Severe the AE produces significant impairment of functioning or incapacitation and is a definite hazard to the subject's health.

These three categories are based on the Investigator's clinical judgment, which in turn depends on consideration of various factors such as the subject's report, and the physician's observations. The severity of the AE should be recorded in the appropriate section of the Adverse Event e CRF.

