### 7.1. STOPPING CRITERIA

Liver chemistry threshold stopping criteria have been designed to ensure subject safety and to evaluate liver event etiology during administration of study drug. Potential discontinuation of study drug for abnormal liver function tests should be considered by the Investigator in consultation with the designated medical monitor if the study subject meets one or more of the following criteria:

- ALT or AST  $\geq 4x$  ULN;
- ALT or AST  $\geq 3x$  ULN and total bilirubin  $\geq 2x$  ULN;
- ALT or AST ≥ 3x ULN if associated with the appearance or worsening of fatigue, nausea, vomiting, right upper quadrant pain or tenderness, fever, rash and/or eosinophilia; or
- ALP elevations, if deemed of liver origin and drug-related as follows:
  - o ALP > 3x ULN;
  - o ALP > 2.5x ULN and total bilirubin > 2x ULN; or
  - o ALP > 2.5x ULN if associated with the appearance or worsening of fatigue, nausea, vomiting, right upper quadrant pain or tenderness, fever, rash and/or eosinophilia.

In the event of discontinuation due to abnormal liver function tests, the subject will be appropriately investigated to determine the potential cause and referred to a physician experienced in the treatment of hepatic disorders.

Study drug should be discontinued if a subject: (1) positively affirms suicidal ideation in response to questions number 4 or 5 in the suicidal ideation section of the C-SSRS, or (2) reports any suicidal behavior or non-suicidal self-injurious behavior since their last visit in response to the C-SSRS Suicidal Behavior questions. The subject should be referred to a psychiatrist or an appropriate health care professional for further evaluation and management.

An additional stopping criterion will be bodyweight loss of  $\geq$  2 kg resulting in a BMI < 18.5.

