### 8.1. Adverse Events

The Medical Dictionary for Regulatory Activities (MedDRA) dictionary (v27.0) will be used for coding AEs on the OLE Adverse Event eCRF.

Analyses of AEs will be performed for those events that are considered treatment emergent (TEAE), where treatment emergent is defined as any AE with onset or worsening on or after the First Study Dose in the OLE study and will be summarized for overall safety population.

The following summary tables will be presented:

- Overall Summary of TEAEs
- TEAEs by system organ class (SOC) and preferred term (PT)
- TEAEs by PT
- TEAEs by SOC, PT, and Maximum Severity
- TEAEs by SOC, PT, and Relationship to Study Drug
- Treatment Emergent Serious AEs (TESAEs) by SOC and PT

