## 8.2. Clinical Laboratory Evaluations

Listings of individual laboratory parameters by visit will not be presented. Significant laboratory results, as assessed by the Investigators, will be tabulated as AEs or SAEs and will appear in individual AE listings.

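### As worded, the AE severity scale grades a symptom-free laboratory result at a liver limit as Mild, and no planned output shows how large the abnormality was

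*Protocol*

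**What the plan says.** **Severity scale.** Protocol 9.2 has three grades. Mild means that "the AE does not interfere in a significant manner with the subject's normal functioning level". Moderate means that "the AE produces some impairment of functioning but is not hazardous to health". Severe means that "the AE produces significant impairment of functioning or incapacitation and is a definite hazard to the subject's health". The section adds that "These three categories are based on the Investigator's clinical judgment", informed by the subject's report and the physician's observations. No grade refers to the size of a laboratory value.

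**When a result becomes an AE.** Protocol 9.1 includes among its examples of AEs "new clinically significant abnormalities in clinical laboratory, physiological testing, or physical examination". SAP 4.1 likewise leaves it to the Investigator whether a result counts as an AE or SAE.

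**What is reported.** Protocol 10.2 planned descriptive summaries of vital signs and laboratory results as change from screening. SAP 3.1 withdraws them. SAP 8.2 drops laboratory listings and says instead: "Significant laboratory results, as assessed by the Investigators, will be tabulated as AEs or SAEs and will appear in individual AE listings". SAP 8.3 to 8.5 treat vital signs, physical examination and ECG in the same way. Among the tables in SAP 8.1 is "TEAEs by SOC, PT, and Maximum Severity", which is Table 14.3.1.4.

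**Liver limits.** Protocol 7.1 states that "Liver chemistry threshold stopping criteria have been designed to ensure subject safety" and gives multiples of ULN for ALT, AST, ALP and total bilirubin. A subject who meets one is considered for discontinuation in consultation with the medical monitor. Discontinuation is not automatic.

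**The concern.** Long-term safety is the study's only objective, and the organ singled out by the nonclinical work is the liver. Protocol 2.2 reports hepatic changes with raised ALP and bilirubin in the six-month rat study. It gives an exposure margin of 1.6-fold on AUC at the no-adverse-effect level, and says the sponsor is still evaluating whether the effects are specific to the rat. Abnormal liver chemistry can be large and still cause no symptoms.

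Once the laboratory summaries and listings are removed, a reader of the safety tables, for instance in the DSUR, has only AE severity as an indication of degree. If severity follows functioning and not magnitude, a trivial enzyme rise and a rise at a liver limit can sit in the same Mild column. An empty Severe column for hepatic terms would then say little about whether anyone reached a limit.

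**Working it through.** The plan states no figure on this point, so the check is a comparison of texts.

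**Step 1: read the scale literally.** Cross impairment (none, some, significant) with hazard to health (no, yes), which gives 3 × 2 = 6 cells, and apply the definitions in Protocol 9.2.

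| Impairment | Not hazardous | Hazardous |
|---|---|---|
| None | Mild | Mild (Moderate and Severe both require impairment) |
| Some | Moderate | No clean fit (Moderate excludes hazard; Severe needs significant impairment) |
| Significant | No clean fit (Severe needs hazard) | Severe |

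The top right cell is the one that matters. Hazard without impairment never lifts an event above Mild.

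**Step 2: see which liver criteria can be met without symptoms.** Protocol 7.1 gives six.

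| Criterion | Further condition |
|---|---|
| ALT or AST ≥4x ULN | None |
| ALT or AST ≥3x ULN with total bilirubin ≥2x ULN | None |
| ALT or AST ≥3x ULN | A listed symptom, sign or eosinophilia |
| ALP >3x ULN | Liver origin and drug-related |
| ALP >2.5x ULN with total bilirubin >2x ULN | Liver origin and drug-related |
| ALP >2.5x ULN | Liver origin and drug-related, plus a listed symptom, sign or eosinophilia |

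Four of six have no symptom condition. Two of those four are purely numerical, and the two ALP criteria also need a judgment of origin and causality. The other two criteria name accompanying findings, but eosinophilia alone, itself a laboratory result, satisfies that part.

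**Step 3: look for another measure of degree.** SAP section 9 lists 9 tables (14.1.1, 14.1.2 and 14.3.1.1 to 14.3.1.7) and 6 listings (16.2.1, 16.2.4 and 16.2.7.1 to 16.2.7.4), so 9 + 6 = 15 outputs. None is a laboratory output. Only Table 14.3.1.4 is organised by grade. If the overall TEAE summary or the AE listings also show severity, it is the same rating on the same scale. General sentences in SAP 6.3.2 and 6.4.1 promise that all data will be listed, but SAP 8.2 to 8.5 and the output list contradict them.

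**Result.** On the wording, a symptom-free result at a liver limit that is reported as an AE fits one grade, Mild. The number of planned outputs showing its magnitude is 0 of 15.

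**The case against.** The strongest reply is that the Investigator decides. Protocol 9.2 rests the grade on clinical judgment, so an Investigator may rate a silent but worrying result above Mild. SAP 6.3.2.1 codes missing severity as severe. This stands, and it means the grade in any one case is not fixed by the text. It does not supply a measure of magnitude, and judgment without an anchor can differ between sites.

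A second reply is that severity and seriousness are separate axes. Protocol 9.4 allows an important medical event to be called serious without loss of function. Such an event would enter Table 14.3.1.6 and Listing 16.2.7.2. It would also appear by preferred term and by relationship and, if it led to study discontinuation, in Listing 16.2.7.3. This stands too: the event need not be invisible. None of these outputs shows how large the abnormality was. The discontinuation table (14.3.1.7) covers serious events only, so a non-serious liver event leading to discontinuation would be identified as such only in a listing.

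A third reply is that the problem bites only because laboratory output was dropped, in an abbreviated SAP for a terminated program with no full CSR expected. That is fair, and it is why the remedy is small.

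A reader might go further and infer that Table 14.3.1.4 is wrong, or that every silent liver-limit result will be tabulated as Mild. The documents support neither. The table would correctly report what Protocol 9.2 defines, and a result not judged clinically significant would not be tabulated at all.

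**Conclusion.** The point holds as a gap in reporting. On the literal scale, hazard does not raise the grade without impairment. A symptom-free result at a Protocol 7.1 liver limit, if reported as an AE, therefore fits only Mild. With laboratory summaries and listings withdrawn, the maximum-severity table is the only output organised by grade for such results, and nothing planned shows their magnitude.

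The extent that can be stated is four of six liver criteria with no symptom condition, and none of 15 outputs showing magnitude. The number of subjects concerned cannot be given. The documents state no rate of liver-limit results, and 180 is an enrolment cap and not the size of the safety set.

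The conclusion assumes that Investigators apply the definitions as written. It is also limited to liver chemistry. A reader might extend it to graded ECG and vital-sign bands, but the documents state no limits from which to build them. The 7.1 limits prompt consideration of discontinuation, so a subject at a limit is not necessarily one who should have stopped drug.

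**What to change.** Before database lock, add one subject-level table and a matching listing to SAP 8.2 and section 9. Give the number and percentage of the Safety population meeting each of these laboratory components at any post-dose sample, whether or not an AE was reported:

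- ALT or AST ≥4x ULN
- ALT or AST ≥3x ULN with total bilirubin ≥2x ULN
- ALP >3x ULN
- ALP >2.5x ULN with total bilirubin >2x ULN

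State whether paired values must come from the same blood sample, since Protocol 7.1 does not say. Note that the ALP rows show the numerical component only, without the judgment of liver origin and drug-relatedness. In the listing, cross-reference the Investigator's severity rating where a matching TEAE exists. Footnote Table 14.3.1.4 to say that Protocol 9.2 severity reflects impairment of functioning and not the size of a laboratory abnormality. Reconcile SAP 6.3.2 and 6.4.1 with 8.2 to 8.5.

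Under SAP 6.3.6 the scheduled study data, which include chemistry, are already in EDC and mapped to SDTM. The cost is therefore modest programming, assuming laboratory reference ranges are held with the results. The other downside is that some results may look less favourable than their Mild label. No visit, test, stopping limit or care rule changes. If the database is already locked, the same outputs can be produced as an identified post-hoc analysis, which SAP 2.2 allows.

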### 9.3. ADVERSE EVENTS - RELATIONSHIPTO STUDY DRUG

The relationship of each AE to the study drug will be based on the Investigator's assessment as to whether there is a reasonable possibility the AE was caused by the study drug. This assessment will be based on the Investigator's clinical judgment, which in turn depends on consideration of various factors such as the subject's report, the timing of the AE in relationship to study drug administration/discontinuation, the Investigator's observations, and the Investigator's prior experience. The Investigator's assessment of the relationship of the AE to the study drug will be recorded in the appropriate section of the EDC.

### 9.4. SERIOUS ADVERSE EVENTS AND UNEXPECTED ADVERSE EVENTS - DEFINITIONS

A Serious Adverse Event (SAE) includes (but is not limited to) an experience occurring at any dose that results in any of the following outcomes:

- Death
- A life-threatening event (i.e., the subject is at immediate risk of death from the reaction as it occurs). "Life-threatening" does not include an event that, had it occurred in a more serious form, might have caused death. For example, druginduced hepatitis that resolved without evidence of hepatic failure would not be considered life-threatening even though drug-induced hepatitis can be fatal.
- In-patient hospitalization (hospital admission, not an emergency room visit) or prolongation of existing hospitalization.
- A persistent or significant disability/incapacity (i.e., a substantial disruption of the subject's ability to carry out normal life functions).
- A congenital anomaly/birth defect.

In addition, medical and scientific judgment should be exercised in deciding whether other situations should be considered an SAE (i.e., important medical events that may not be immediately life-threatening or result in death but may jeopardize the subject or may require medical or surgical intervention to prevent one of the other outcomes

listed in the definition above). Examples of such medical events include (but are not limited to): allergic bronchospasm requiring intensive treatment in an emergency room or at home, blood dyscrasias or convulsions that do not result in in-patient hospitalization, or the development of drug dependency or drug abuse.

An **unexpected** AE is one for which the specificity or severity is not consistent with the current Investigator's Brochure (IB). For example, hepatic necrosis would be unexpected (by virtue of greater severity) if the Investigator's Brochure only listed elevated hepatic enzymes or hepatitis.

Similarly, cerebral thromboembolism and cerebral vasculitis would be unexpected (by virtue of greater specificity) if the Investigator's Brochure only listed cerebral vascular accidents.

